### 11.5.3 Exploratory efficacy analysis

#### 11.5.3.1 Overall survival (OS)

OS is defined as the time from the start of randomization to the death of the subject caused by any reasons. Survival curves will be plotted using the Kaplan-Meier method and the 95% CI for median time will be calculated using the Brookmeyer-Crowley method. The 6-month, 9-month, and 12-month OS rates and their 95% CIs in the two cohorts will be estimated.

Censoring rules: For subjects who are still alive at the last follow-up, their OS will be censored at the date of last follow-up. For subjects who are lost to follow-up, their OS will be censored at the last confirmed survival time before lost to follow-up. The censored OS is defined as the time from randomization to censoring. OS will be calculated in months using the following formula: (Date of OS event or censored date - date of randomization + 1)/30.4375.

### **11.5.3.2 Time to objective response (TTOR)**

TTOR is defined as the period of time from the start of randomization to the first documented BOR of objective response (as per RECIST 1.1).

TTOR will only be measured in subjects with a BOR after treatment. The date of response is the date of first documented response but not the date of confirmation. TTOR will be statistically described by the number of subjects, mean, standard deviation, median, minimum, and maximum.

### **11.5.3.3 Subgroup analysis of ORR, PFS, and OS**

The subgroup analysis is exploratory and will only be performed based on FAS. This study includes the following subgroups:

- Length of chemotherapy cycles ( $\leq 4$  cycles vs.  $> 4$  cycles) (only in cohort 1)
- Age ( $< 60$  vs.  $\geq 60$ )
- Gender (male vs. female)
- Baseline ECOG PS score (0 vs. 1)
- Peritoneal metastasis (yes vs. no)
- Liver metastasis (yes vs. no)
- Metastasis sites ( $\leq 2$  vs.  $> 2$ )
- History of radical gastrectomy (yes vs. no)
- Lesion site (stomach vs. gastroesophageal junction)

In order to explore the impact of subgroup factors on the ORR, the ORR and its two-sided 95% exact CI (Clopper-Pearson) in each subgroup of a single cohort will be calculated. The PFS and OS for each subgroup of a single cohort will be plotted using the Kaplan-Meier method and the 95% CI for median time will be calculated using the Brookmeyer-Crowley method.

## **11.6 Statistical Analysis of PK**

Descriptive statistical analysis will be performed for the PK drug concentrations of SHR-1210 and apatinib.

## **11.7 Statistical Analysis of PD**

Not applicable

## **11.8 Statistical analysis of immunogenicity (ADA)**

The number and percentage of subjects with positive ADA and negative ADA will be summarized using descriptive statistics.

For the population with positive ADA, the following items will be analyzed: the onset of ADA positive, the number and percentage of subjects with transient positive post-baseline results (transient ADA positive is defined as the subjects who are negative at baseline and have only one ADA-positive sample post baseline before the last sample and are not persistent ADA positive), the number and percentage of subjects with persistent positive post-baseline results (persistent ADA positive can be divided to two categories: 1) negative at baseline, there are at least two positive samples post baseline, where the first and last ADA-positive samples are separated by a period  $>16$  weeks, or 2) negative at baseline, the last post-baseline sample is positive, or the last post-baseline sample is negative and the second last post-baseline sample is positive), and the number and percentage of subjects with other positive post-baseline results (other ADA positive is defined as the subjects who are negative at baseline, have at least two ADA positive samples post baseline, but not persistent ADA positive, and the last sample is negative).

In the meantime, the safety of ADA-positive and negative subjects will be summarized so as to investigate the effects of ADA on safety. ADA-positive subjects refer to subjects with post-baseline ADA-positive samples, mainly including: a: the subjects who have the baseline negative and post-baseline positive samples, or b. the subjects who have both baseline and post-baseline positive samples, and the titer of the post-baseline samples is  $\geq 4$ -fold of the baseline titer. ADA-negative subjects are those who are not ADA positive.

The number and percentage of subjects with neutralizing antibodies (Nabs) positive will be summarized using descriptive statistics.

Immunogenicity raw data will be reported in the form of listing.

## 12 APPENDICES

### Appendix 1.1 Time Point Response: Subjects with Target Lesions (Including or Excluding Non-Target Lesions)

Target Lesion	Non-Target Lesion	New lesion	Overall Response at the Time Point
CR	CR	Non	CR
CR	Non-CR/Non-PD	Non	PR
CR	Not evaluable	Non	PR
PR	Non-PD or not all evaluable	Non	PR
SD	Non-PD or not all evaluable	Non	SD
Not all evaluable	Non-PD	Non	NE
PD	Any	Yes or No	PD
Any	PD	Yes or No	PD
Any	Any	Yes	PD

CR = complete response, PR = partial response, SD = stable disease, PD = progressive disease, and NE = not evaluable

### Appendix 1.2 Time Point Response - Subjects with Non-target Lesions Only

Non-Target Lesion	New lesion	Overall Response
CR	Non	CR
Non-CR/Non-PD	Non	Non-CR/Non-PD a
Not all evaluable	Non	Not evaluable
Equivocal PD	Yes or No	PD
Any	Yes	PD

a: "Non-CR/non-PD" is preferred over SD for non-target disease. Since SD is increasingly used as an endpoint for response evaluation, non-CR/non-PD response is developed to address the absence of lesion measurability.

### Appendix 1.3 Best Overall Response with CR and PR to Be Confirmed

Evaluation at the Previous Time Point	Evaluation at the Subsequent Time Point	BOR
CR	CR	CR
CR	PD, missing	SD (> 6 weeks from the start of treatment (5 weeks after subtracting 1 week of visit window))
CR	PR or SD a	
Note: This situation generally will not occur.
 
 
• If the last evaluation is CR, then a little bit of the lesion in the next evaluation will lead to the response evaluation of PD. The BOR depends on whether the minimum time of 6 weeks for SD is met. If met, it is SD.
 

Evaluation at the Previous Time Point	Evaluation at the Subsequent Time Point	BOR
PR	PR, unconfirmed CR	PR
PR	SD, missing	SD
PR	PD	SD (> 6 weeks from the start of treatment (5 weeks after subtracting 1 week of visit window))
SD	SD, unconfirmed	SD
	PR, unconfirmed CR	
SD	NE → SD	SD
PR	NE → PR	PR
NE	NE	NE

CR = complete response, PR = partial response, SD = stable disease, PD = progressive disease, and NE = not evaluable.

a: If a CR is truly met at first time point, then any disease seen at a subsequent time point, even the disease meeting PR criteria relative to baseline, makes the disease PD at that point (since disease must have reappeared after CR). Best overall response will depend on whether minimum duration for SD is met. However, sometimes CR may be claimed when subsequent scans suggest small lesions are likely still present and in fact the subject have PR, not CR at the first time point. Under these circumstances, the original CR should be changed to PR and the best overall response is PR.

#### Appendix 1.4 Rules for Imputing Incomplete Dates of AE and CM:

Date	Start Date	End Date
Missing "Day"	Impute with the start day of study treatment when the year and month of the occurrence are identical to those of study treatment; otherwise, impute with the first day of the corresponding month	Impute with the last day of the month
Missing "Month" and "Day"	Impute with the start month and day of study treatment when the year of the occurrence is identical to that of study treatment; otherwise, impute with "1 Jan."	31 Dec.
Missing "Year", "Month", and "Day"	No imputation	No imputation

Note: All imputed dates must be before the date of end/termination of study and date of death.

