#### Secondary endpoints:

- **Progression free survival (PFS):** the time from the start of study treatment (the time of the first administration provided by the investigator) to the time of objective progressive disease or death due to any cause, whichever occurs first.
- **Duration of response (DoR):** the time from first evidence of CR or PR until first evidence of disease progression or death due to any cause. The date of response is the date of first documented response rather than the date of confirmation.
- **Disease control rate (DCR):** the percentage of participants in the analysis population who have CR, PR, or stable disease (SD).

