### 11.4.1 Adverse event

An adverse event (AE) refers to any untoward medical occurrence in a study subject administered a medicinal product and which does not necessarily have a causal relationship with this treatment. In this study, AE should be collected from the signing of informed consent form (ICF) to 90 days after the last dosing of study drugs. AE includes any adverse symptom or sign, laboratory test abnormality, or disease. AE will be summarized separately in different stages of cohort 1 (SHR-1210 + capecitabine + oxaliplatin, sequence by SHR-1210 + apatinib mesylate, and total) and cohort 2.

AE will be analyzed based on treatment-emergent adverse event (TEAE). TEAE is defined as an AE that occurs or becomes aggravated on the same day or after the first dosing of study drugs but not later than 90 days after the last dosing of study drugs. Only TEAE will be summarized and analyzed. A separate data listing will be provided only for AE that occurs before treatment.

Each AE will be coded by MedDRA (v23.0) and graded by NCI-CTCAE v4.03. For the same SOC and/or PT, multiple cases of the same events that occur in one subject will be counted only once. For the same AE reported in one subject multiple times but varying in CTCAE grade, the greatest grade episode will be enumerated.

A summary description report will be provided for the number and percentage of subjects experiencing at least one TEAE, treatment-related TEAE (SHR-1210, oxaliplatin, capecitabine, and apatinib), severe TEAE (CTCAE Grade  $\geq 3$ ), TEAE leading to study drug discontinuation/interruption, treatment-related TEAE leading to drug discontinuation/interruption, TEAE leading to dose modification of study drugs, treatment-related TEAE leading to dose modification of the study drugs, TEAE leading to subject withdrawal from treatment, serious adverse event (SAE), and death.

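### SAP Appendix 1.4 imputes AE start dates without checking the AE's own end date, so an event that ended before first dose can be counted as treatment-emergent

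*SAP*

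**What the plan says.** SAP 10.2 sends incomplete AE and concomitant medication dates to Appendix 1.4. For start dates the appendix gives these rules:

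- Day missing, month and year equal to those of treatment start: "Impute with the start day of study treatment when the year and month of the occurrence are identical to those of study treatment".
- Day missing, any other month: "otherwise, impute with the first day of the corresponding month".
- Month and day missing: "Impute with the start month and day of study treatment when the year of the occurrence is identical to that of study treatment"; in any other year, 1 January.
- Nothing recorded: no imputation.

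The only limit is the note under the table: "All imputed dates must be before the date of end/termination of study and date of death". The appendix does not define treatment start, but the PFS definition in SAP 9.1 ties it to one date per subject: "the start of study treatment (the time of the first administration provided by the investigator".

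SAP 11.4.1 sets how the dates are used. On collection: "AE should be collected from the signing of informed consent form (ICF) to 90 days after the last dosing of study drugs". On classification: "TEAE is defined as an AE that occurs or becomes aggravated on the same day or after the first dosing of study drugs". Only treatment-emergent AEs (TEAEs) are summarised; events before treatment go to a separate listing. For cohort 1, "AE will be summarized separately in different stages of cohort 1", that is, for the chemotherapy stage, the apatinib stage and the total.

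**The concern.** Moving an onset of unknown day to the first-dose date is a usual conservative choice when the event could have begun on either side of dosing. Here the rule also applies when the record shows that it could not. An AE with a complete end date before first dose began and finished without any study drug. The appendix still dates its start to first dose, and SAP 11.4.1 then makes it a TEAE.

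Such records are foreseeable, because collection starts at consent and SAP 3.1 allows a screening period of up to 28 days. At stake are TEAE counts that may include events finished before any drug was given, and records whose start falls after their end. No efficacy result is touched.

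**Working it through.** The plan states no figure to reproduce. The check applies the written rule to dates.

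**Inputs.** F = first-dose date. E = AE end date. Start rules and the single limit: SAP Appendix 1.4. TEAE definition and collection from consent: SAP 11.4.1. Screening of at most 28 days: SAP 3.1.

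**1. Worked example, day missing.** F = 20 March 2018, AE start 'March 2018', E = 5 March 2018.
- The screening window reaches back to 20 March − 28 days = 20 February, so an AE in early March can fall after consent.
- The possible onset dates are 1 to 5 March, which are 19 to 15 days before F. None is on or after F.
- Month and year match F, so the imputed start is 20 March, 15 days after E.
- Imputed start ≥ F, so the event is a TEAE. The note on study end and death does not prevent this.

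**2. Worked example, year only.** Same F, AE start '2018', E = 12 March 2018. The year matches, so the imputed start is again 20 March, after E, and the event is a TEAE.

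**3. Where the conflict can arise.** When the rule gives the first of the month or 1 January, the imputed start is the earliest possible date and cannot be later than E. When the rule gives F, the start is later than E exactly when E < F. A check against E therefore changes only events that ended before first dose. Ambiguous events keep the conservative default. The check also works for partial end dates: the appendix sets these to the last day of the month or to 31 December, the latest possible end, so if that date precedes F the event certainly ended before dosing.

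**4. How often, given such a record.** Take AEs with a partial start, true onset 1 to 28 days before F and E < F. Weight all onset days equally, over 365 consecutive first-dose dates from 15 December 2017 (assumptions; roughly the planned enrolment year in Protocol section 14). There are 365 × 28 = 10,220 combinations.
- Day missing: a first dose on day D of a month has min(28, D − 1) onset days in the same month. These sum to 462 for a 31-day month, 434 for a 30-day month and 378 for February. Total: 7 × 462 + 4 × 434 + 378 = 5,348; 5,348 / 10,220 = 52%.
- Year only: the rule misses only onsets in the previous year, which arise for first doses on 1 to 28 January: 28 + 27 + … + 1 = 406. (10,220 − 406) / 10,220 = 96%.

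These shares are conditional on having such a record. They say nothing about how many there will be.

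**5. Secondary note on cohort 1 stages.** The switch to apatinib comes after 4 to 6 cycles of 21 days, that is 84 to 126 days after F, so the first-dose-month clause cannot apply in the switch month. The other two clauses can matter. With F = 20 March 2018 and 4 cycles, the switch is on 12 June. A true onset on 17 June becomes 1 June if the day is missing and 20 March if only the year is known. Both dates lie in the chemotherapy stage. Day-missing onsets in later months are placed correctly.

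**The case against.** The strongest reply is that few such records will reach the analysis. Protocol 7.2.1 has AE start and end dates collected. Protocol 12.1.2 requires all items to be completed and runs logic checks that raise queries. Protocol 12.2.3 adds a review of missing values before lock. SAP 11.4.1 counts a subject once per system organ class or preferred term, so an extra record often changes no count. All of this stands as a reason to expect a small effect. None of it corrects the rule, which gives a wrong result for the records that remain.

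A reader might infer more than the documents support:

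- *AE durations will be distorted.* In the example, end − start + 1 = 5 − 20 + 1 = −14 days. But the SAP plans no AE-duration summary; the only related duration in 11.4.1 is that of steroid dosing. The impossible record is a data-integrity fault and does not bias a planned table.
- *The errors all run one way, or apatinib toxicity is understated.* The TEAE error adds events. The stage error, where it occurs, removes events from the apatinib stage. Cohort 2 has no switch, so there the rule can only add. TEAEs are also summarised by relation to each study drug, and that summary does not depend on stage.
- *The stage tables are certainly affected.* This assumes that stage follows the imputed onset date, which the SAP does not state.
- *Partial dates compatible with apatinib should all go to the apatinib stage.* That creates the opposite bias. With a switch on 25 April, only 6 of 30 April days are on apatinib, yet every 'April' event would move there. If done only for the stage tables, it would also give one AE two onset dates.

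**Conclusion.** The point holds for AEs with a partial start whose known month or year matches first dose and whose end date is before first dose. For these, Appendix 1.4 overrides a known fact and SAP 11.4.1 turns the result into a TEAE. This follows from the text alone.

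The number of records affected cannot be derived. The documents give neither the share of partial AE dates nor an AE count, and any figure per cohort would rest on an assumed rate. The number is probably small and could be zero. The 52% and 96% above assume equally weighted onset days and apply only once such a record exists. Severity is minor.

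The stage matter is a side note. The SAP does not say how a partially dated AE is assigned to the chemotherapy or apatinib stage of cohort 1. If stage follows the imputed onset, day-missing onsets in the switch month (unless the switch is on the 1st) and year-only onsets in the first-dose year default to chemotherapy.

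**What to change.** Add to Appendix 1.4: an imputed AE start may not be later than the AE's end date. If the end date is before first dose, the start is the later of the consent date and the earliest date compatible with the recorded part, and the event is classed as pre-treatment and appears in the listing only.

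In the first example, with consent on 26 February (illustrative), the start becomes the later of 26 February and 1 March, which is 1 March. It precedes the end on 5 March, and the event stays out of the TEAE tables. Among events ending before first dose, the share wrongly classed as TEAEs falls to 0%.

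The cost is two sentences in the SAP before database lock and minor programming. Ambiguous onsets, the response analyses, sample size and trial conduct are unchanged.
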